8.2.4 Clinical safety laboratory assessments

See Section 10.2 for the list of clinical laboratory tests to be performed and to the SoA for the timing and frequency.

The investigator must review the laboratory report, document this review, and record any clinically significant changes occurring during the study as an AE. The laboratory reports must be filed with the source documents.

Abnormal laboratory findings associated with the underlying disease are not considered clinically significant unless judged by the investigator to be more severe than expected for the participant's condition.

All laboratory tests with values considered clinically significantly abnormal during participation in the study or within one month after the last dose of study intervention should be repeated until the values return to normal or baseline or are no longer considered clinically significant by the investigator or the medical monitor.

If such values do not return to normal/baseline within a period of time judged reasonable by the investigator, the etiology should be identified, and the sponsor notified.

All protocol-required laboratory tests, as defined in Section 10.2, must be conducted in accordance with the laboratory manual and the SoA.

09 FEB 2023 Page: 53 of 95

If laboratory values from non-protocol specified laboratory tests performed at the institution's local laboratory require a change in participant management or are considered clinically significant by the investigator (e.g. SAE or AE or dose modification), then the results must be recorded.

Clinically relevant changes, especially when resulting in a decision against dose titration, are to be documented as AE, with details on the respective lab results provided in the comment field of the AE page in the eCRF.

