In case of clinically relevant abnormal laboratory results, the investigator has the discretion to perform unscheduled repeat laboratory examinations earlier than at the intervals provided in the SoA in Section 1.3. These unscheduled examinations should be processed by the central lab to ascertain that the data will be included in the database. At the investigator's discretion, additional laboratory parameters may be investigated and samples may be processed by the local lab. In case of relevant liver enzyme elevation (see also Section 10.5), the investigator should perform a repeat serum chemistry panel 2 times per week (including serum transaminases [AST and ALT] and serum bilirubin), frequency of retesting can decrease to once a week if laboratory abnormalities decrease and participant is asymptomatic.

Estimation of glomerular filtration rate (eGFR)

eGFR will be calculated using CKD-EPI formula, using the serum creatinine concentration measured at screening (Kidney Disease: Improving Global Outcomes (KDIGO) CKD Work Group 2013). The calculation will be done by the central laboratory. In case of a decrease by \geq 40%, a critical alert will be provided to the investigator, as it may represent a reason for treatment discontinuation, as described in Section 7.1.2.

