10.2 Appendix 2: Clinical laboratory tests

The tests detailed in Table 10-1 will be performed by a central laboratory apart from urine pregnancy test, that will be performed locally.

Investigators must document their review of each laboratory safety report.

The laboratory parameters to be analyzed are defined in Table 10-1. The time points of analysis are defined in the schedule of activities.

Additional laboratory tests (see Table 10-4 for examples) may be performed as deemed appropriate by the Investigator, e.g. in case of signs of liver toxicity.

09 FEB 2023 Page: 71 of 95

Table 10-1 Protocol-required laboratory tests

		Parameters (by category)	Sample destination
Blood / plasma / serum	Hematology	Leukocytes, Erythrocytes, Hemoglobin, Hematocrit, HbA1c, Mean corpuscular volume (MCV), Mean corpuscular hemoglobin (MCH), Platelets, Neutrophils, Eosinophils, Basophils, Lymphocytes, Monocytes	Central laboratory
	Biochemistry	Alanine aminotransferase (ALT), Aspartate aminotransferase (AST), Gamma-glutamyl transferase (GGT), Alkaline phosphatase (AP), Total bilirubin (if elevated: differentiation of direct bilirubin), Lactate dehydrogenase (LDH), Creatinine, Urea, Creatine kinase, Chloride, Potassium, Sodium, Calcium, Phosphate, Glucose, Total protein, Albumin, Triglycerides, Cholesterol (total, LDL, HDL), ß-hCG (women)	Central laboratory
	Plasma PK	BAY 1101042 and its metabolites M1, M6 and M7	Central laboratory
	Biomarkers in plasma/serum	See Section 8.6.1 for details	Central laboratory
	Hormones	Thyroid stimulating hormone (TSH)	Central laboratory
Urine		ß-hCG pregnancy test (women)	Local evaluation

HDL = high-density lipoprotein, LDL = low-density lipoprotein; PK = pharmacokinetics; HbA1c= hemoglobin A1c (glycated hemoglobin); β-hCG = β-subunit of human chorionic gonadotropin

09 FEB 2023 Page: 72 of 95

10.3 Appendix 3: AEs and SAEs: Definitions and procedures for recording, evaluating, follow-up, and reporting

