- Obtaining a history of concomitant drug use (including nonprescription medications and herbal and dietary supplement preparations), alcohol use, recreational drug use, and special diets.
- Investigation of potential alternative causes of liver disease. This may include ruling
 out liver injury by acute viral infection, autoimmune or alcoholic hepatitis;
 nonalcoholic steatohepatitis; hypoxic/ischemic hepatopathy and biliary tract disease.
 This may require performing additional procedures, e.g. ultrasound examinations or
 laboratory examinations, including but not limited to those listed in Table 10-4. If
 requested, tests will be done retrospectively using residual blood/serum samples
 collected at visits before laboratory abnormalities occurred.
- Obtaining a history of exposure to environmental chemical agents.
- Obtaining additional tests to evaluate liver function as required, as outlined in a separate liver injury follow-up questionnaire.

09 FEB 2023 Page: 80 of 95

Table 10-4 Laboratory examinations for workup of liver safety findings

Parameters

Albumin

Alkaline phosphatase (AP)

Alanine-aminotransferase (ALT)

Aspartate-aminotransferase (AST)

Bilirubin: total, direct

Complete blood count including differentials

Cholesterol (total, LDL, HDL)

Cholinesterase

Conjugated (direct) bilirubin

Creatine kinase (CK)

Gamma-glutamyltransferase (γ -GT = GGT)

Glutamate dehydrogenase (GLDH)

Hemoglobin

International normalized ratio (INR)

Lactate dehydrogenase (LDH)

Prothrombin time (Quick) (PT)

Triglycerides

Anti-Hepatitis A virus Antibodies

Hepatitis B virus (HB): surface antigen (HBs), anti-HBs, anti-HB core antibodies (IgM, IgG), HB PCR

Anti-Hepatitis C virus (HCV) antibodies, HCV PCR

Anti-Hepatitis D virus (HDV) antibodies (if positive, automatically test HDV RNA)

Anti-Hepatitis E virus (HEV) IgM (if positive, automatically test HEV RNA)

Anti-Cytomegalovirus (CMV) IgM Antibodies

Anti-Epstein-Barr Virus (EBV) IgM Antibodies

Herpes simplex IgM (anti HSV IgM)

SARS-COV-2 antibodies

Immunoglobulins: (Ig) G level (gamma globulins), IgA, IgM

Antineutrophil cytoplasmic antibodies (c-ANCA, p-ANCA)

Anti-mitochondrial antibodies

Anti-native double-stranded DNA Antibodies

Anti-Smith Antibodies

Alpha-1 antitrypsin (A1AT) level

Ceruloplasmin

Ferritin

Iron

Total iron binding capacity (TIBC)

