#### 4. Statistical Analyses

#### 4.1 General Considerations

#### 4.1.1 General Principles

The SAP will be finalized prior to unmasking.

The statistical evaluation will be performed by using the software SAS (release 9.4 or higher; SAS Institute Inc., Cary, NC, USA) and R (version 3.5.2 or higher; R Foundation for Statistical Computing, Vienna, Austria).

All data will be listed and summarized in tables. Graphical illustrations will be provided by treatment group (runcaciguat, placebo) where appropriate. Summary statistics will be presented for the participants treated with runcaciguat and for the participants treated with placebo. Descriptive statistics by visit will be provided for the original data as well as for change from baseline, where applicable. Additional summary statistics per dose of runcaciguat administered will be presented, where meaningful. Doses may be grouped to reach more meaningful sample sizes. Frequency tables will be provided for qualitative data.

Continuous variables assumed to be normally distributed will be summarized using the number of participants, mean, standard deviation, minimum, lower quartile, median, upper quartile and maximum. The geometric mean and SD will be provided additionally for the variables where log-normal distributions are assumed.

Generally, data will be analyzed comparing the two intervention groups against each other.

Furthermore, for the runcaciguat treatment group, summary statistics by visit for continuous variables will be further broken down by the actual maintenance dose level, i.e., the dose level reached after the end of the titration phase (at Visit 6) (in case a sufficient number of patients pertains to this dose level).

Data from unscheduled measurements will be listed, but not included in summary statistics or frequency tables.

Listings will be provided sorted by treatment group (runcaciguat, placebo), DRSS at baseline (47, 53) and participant identifier.

Baseline is defined as the last pre-dose assessment before first study intervention.

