#### 4.5.3 Laboratory assessments

- HbA1c
- Triglycerides
- HDL- / LDL-/ total serum cholesterol
- Further parameters are detailed in Section 10.2 of the CSP

Continuous laboratory values will be summarized descriptively by parameter including absolute changes from baseline. Frequency tables will be provided for qualitative data.

In addition, the frequencies for liver abnormality criteria as defined in CSP Section 10.5 will be presented:

- ALT or AST  $>3 \times ULN$ ,
- ALT or AST >3 x ULN and Total bilirubin >2 x ULN,

- ALT or AST >3 x ULN and INR >1.5 x ULN,
- ALT or AST >5 x ULN for more than 2 weeks,
- ALT or AST >8 x ULN.

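### The SAP's ban on unscheduled values in frequency tables has no exception for the liver-criteria table, so its INR row has no scheduled INR and three other rows can undercount

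*SAP*

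**What the plan says.** SAP 4.1.1 (General Principles) sets a rule for the whole plan: "Data from unscheduled measurements will be listed, but not included in summary statistics or frequency tables". SAP 4.5.3 (Laboratory assessments) says that "the frequencies for liver abnormality criteria as defined in CSP Section 10.5 will be presented" and lists five rows:

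- either enzyme above 3 x ULN
- the same with total bilirubin above 2 x ULN
- an INR row: "ALT or AST >3 x ULN and INR >1.5 x ULN"
- a duration row: "ALT or AST >5 x ULN for more than 2 weeks"
- a row for either enzyme above 8 x ULN

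Neither 4.5.3 nor SAP 4.8 (changes to planned analyses) exempts this table from 4.1.1. SAP 4.1.3 speaks generally of using all valid observed data, but 4.1.1 is the specific rule for unscheduled values.

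Protocol 8.2.4 calls the repeat liver panels unscheduled and makes sure that they are captured: "These unscheduled examinations should be processed by the central lab to ascertain that the data will be included in the database". INR is not among the protocol-required tests in Table 10-1. It appears in Table 10-4, the liver work-up list, whose tests are optional under protocol 10.2: "Additional laboratory tests (see Table 10-4 for examples) may be performed as deemed appropriate by the Investigator". Results from non-protocol tests run locally must be recorded when those from the institution's "local laboratory require a change in participant management or are considered clinically significant by the investigator".

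SAP 4.1.2 derives an End-of-Treatment value from the visit on the last treatment day or, failing that, the first visit afterwards. SAP 4.1.4 keeps laboratory values from early-discontinuation visits, and from visits after stopping treatment, out of summary statistics. It does not mention frequency tables.

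**The concern.** Four of the five rows are criteria that the protocol expects to be followed up, and often established, by retests or work-up tests. The general rule removes exactly those data. A participant can meet a criterion on central-laboratory retests already in the database and still not be counted in the row for that criterion.

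The INR row is the clearest case. With no scheduled INR, it can only report zero, and a reader will take that zero as evidence that no such case occurred.

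At stake is the accuracy of one descriptive safety table. Liver enzyme elevation is a named risk in protocol Table 2-2 and suspected hepatic injury is an adverse event of special interest (AESI), so the table is likely to be read.

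**Working it through.** The documents give no figure for this table. The check sets each row against the data that 4.1.1 leaves available, then looks at sampling intervals.

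**Inputs (protocol Tables 1-2 to 1-4).** Scheduled biochemistry at the 13 post-dose treatment visits, Visits 3 to 15, falls on Days 8, 15, 22, 29, 43, 57, 85, 113, 141, 169, 225, 281 and 337. Nominal gaps are 7, 7, 7, 14, 14, 28, 28, 28, 28, 56, 56 and 56 days. Windows are ±7 days from Visit 9 onward.

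**INR row.** Scheduled visits with INR: 0 of 13. Under 4.1.1 the row has nothing to draw on.

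**>8 x ULN and bilirubin rows.** A qualifying value at a scheduled visit is counted. One that appears only at a retest is not. Hypothetical example: ALT is 4 x ULN at a scheduled visit and 9 x ULN on retest, and the participant is correctly withdrawn. The table counts this person under >3 x ULN and not under >8 x ULN.

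**Duration row.** Scheduled values alone must supply two results above 5 x ULN more than 14 days apart.

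- Visits 12 to 15: the nominal gap is 56 days, and the shortest gap the windows allow is 56 − 7 − 7 = 42 days. An excursion starting at or after Visit 12 and lasting 15 to 41 days meets the criterion but cannot contain two scheduled on-treatment values. This interval is 337 − 169 = 168 days, and 168/336 = 50% of treatment.
- Visits 8 to 12: the nominal gap is 28 days, so on nominal days an excursion of 15 to 27 days cannot contain two scheduled values. Windows change the gap to 19–37 days (Visit 8 to 9) or 14–42 days (Visits 9 to 12).

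**Illustration only.** Assume onset uniform over treatment, values continuously above 5 x ULN for D days, first detection at a scheduled visit, then retests every 3.5 days. The first retest beyond 14 days is at 17.5 days. Simulated on nominal visit days (400,000 excursions per case), with missed share = 1 − (captured ÷ demonstrable from all dated values):

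| | D = 28 | D = 42 |
|---|---|---|
| Demonstrable from all dated values | 36.3% | 69.2% |
| Captured by scheduled values only | 4.5% | 28.6% |
| Missed, End-of-Treatment value not counted | 1 − 4.5/36.3 = 88% | 1 − 28.6/69.2 = 59% |
| Missed, End-of-Treatment value 7 days after the withdrawing retest | 56% | 21% |
| Missed, 3.5 days after | about 25% | about 10% |
| Missed, same day | 0% | 0% |

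Spreading visits over their windows lowers the third row to about 70% and 56%. At D = 60 with the End-of-Treatment value 3.5 days later, about 3% are missed; at D = 90, essentially none. The answer is driven by excursion length and by when an End-of-Treatment sample is taken, and the documents specify neither.

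**The case against.** The strongest reply is that the information is reported elsewhere. Protocol 9.4.5 promises listings with flags and additional tables of all abnormal laboratory values, without limiting them to scheduled samples. SAP 4.5.2 tabulates hepatic AESIs and adverse events leading to permanent discontinuation. SAP 4.5.1 reports dose modifications with reasons for withdrawal, and SAP 6.3 reports reasons for stopping treatment. Unscheduled values are listed. SAP section 1 places the TLF specification in a separate document, which may already contain an exception. All of this stands and lowers the weight. It does not correct the table: adverse event outputs depend on what the investigator reports, and abnormal-value tables are not said to apply the combined or duration criteria.

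A second reply is that the End-of-Treatment value may rescue the duration row, because 4.1.4 bars such values only from summary statistics. With frequent retests, the first visit after the last dose could come within days. That is fair, and it is why the point is conditional for this row. It does not help if enzymes have fallen by then, and protocol 7.1.1 sets no deadline for that visit.

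Three stronger readings are tempting but not supported:

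- **That the table miscounts withdrawals.** It is a table of abnormality criteria. Its first row triggers only close observation, and it omits the symptom-based withdrawal criterion in protocol Table 10-3, so it is not a full count of withdrawals.
- **That the two-sample confirmation rule in protocol 7.1.1 itself proves a loss.** If the scheduled value already exceeds the threshold, the row is filled whatever the retest shows.
- **That protocol 10.5 and 8.2.4 conflict on retest frequency.** Section 10.5 sets an upper limit and 8.2.4 a definite frequency. Following 8.2.4 satisfies both.

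**Conclusion.** The point holds as a low-end minor defect. Read as written, the plan leaves the INR row without any scheduled INR. It drops retest-only cases from the >8 x ULN and bilirubin rows, and it can miss cases in the duration row unless an End-of-Treatment value taken while ALT or AST is still raised is counted. The first two statements follow directly from the text; the third depends on how SAP 4.1.2 and 4.1.4 are applied. All three assume that the TLF specification adds no exception.

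A reader might infer from the illustration that most prolonged elevations would go uncounted. The documents do not support a figure: the missed share runs from 0% to 88% across the assumptions shown, and no event rate is given. Protocol 2.3.1 reports no evidence of hepatic toxicity in the completed chronic kidney disease study, so few participants, perhaps none, are likely to be affected. The primary endpoint and the proof-of-concept decision are not touched.

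**What to change.** In SAP 4.5.3:

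1. Derive every liver-criteria row from all dated post-baseline values: scheduled, unscheduled, End-of-Treatment and post-discontinuation, including recorded local INR. State this as an explicit exception to SAP 4.1.1 and 4.1.4.
2. Count the duration row when the first and last values above 5 x ULN are more than 14 days apart, with no value at or below 5 x ULN between them.
3. Beside the INR row, show the number of participants with any INR measured, so that a zero can be read correctly.

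The cost is one derivation rule and one extra count. ALT, AST and bilirubin retests processed by the central laboratory as protocol 8.2.4 asks are already in the database. The INR row must also read locally recorded results. No new sampling is required, and protocol 10.5 needs no change.

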#### 4.1.2 End of Treatment

Beside the Visit 15 EoT, the EoT values will also be derived to account for eCRF entry errors. The EoT value is the value of the visit at the last treatment day. In case no visit occurred at the last treatment day, the EoT value is the value of the first visit after last treatment.

#### 4.1.3 Missing Data

For handling of missing data for the primary efficacy endpoint, see Section 5.3.2.

Statistical analysis will be based on the available data. Analysis will be performed considering all valid data observed for the respective analysis sets. All missing or partial data will be presented in the subject data listing as they are recorded on the CRF.

Date of first dose of study intervention is defined as the date of first dose from the appropriate CRF page capturing the study intervention (runcaciguat or placebo) if this date is complete. Date of last dose of study intervention is defined as the date of last dose from the appropriate

CONFIDENTL	٩L
COLUMN TO DIVIN	

CRF page capturing the study intervention if this date is complete. If the first and the last dose dates are missing or incomplete, we will consider the following scenarios for imputation of missing dates:

First dose date is missing or incomplete	Imputation rule	
Only day of first dose date is missing	Impute the first dose date as maximum of the	
	date of randomization and first day of month.	
Month and day of first dose date are missing	Impute the first dose date as randomization date.	
First dose date is completely missing but last	Impute the first dose date as randomization date	
dose date is available	but no later than the date of last dose.	
First dose date and last dose date are missing	Impute the first dose date as randomization date if tablet boxes were dispensed and if these tablet boxes were not returned unused.	
Last dose date is missing or incomplete	Imputation rule	
Only day of last dose date is missing	
 
Impute the last dose date using last day of the month.
 
Derive last dose date as minimum of (imputed last dose date, the date of death, the last visit date before follow-up) but no earlier than the date of first dose.
 
	
Month and day of last dose date is missing	
 
Impute the last dose date using last day of the year.
 
Derive last dose date as minimum of (imputed last dose date, the date of death, the last visit date before follow-up) but no earlier than the date of first dose.
 
	
Last dose date is completely missing but first dose date is available or can be imputed	Impute last dose date as minimum of (the date of death, or the last visit date) but no earlier than the date of first dose.	

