7.1 Discontinuation of study intervention

7.1.1 Permanent discontinuation

In rare instances, it may be necessary for a participant to permanently discontinue (definitive discontinuation) study intervention. If study intervention is permanently discontinued, an End-of-Treatment visit should be performed in line with Visit 15. The participant remains in the study for continued assessment of study outcomes following the visit schedule in section 1.3.

Unscheduled visits may be performed as deemed appropriate by the investigator, in particular in case of withdrawal because of an adverse event.

Participants *must* be withdrawn from the *study intervention* for any of the following reasons:

- Increases in transaminases as described in Table 10-3 (confirmed by analysis of two blood samples; additional laboratory examinations may be performed if necessary):
- Safety concerns for a participant by the investigator or the sponsor, e.g. due to obvious non-compliance.
- Pregnancy (see Section 8.3.5 for details)
- Temporary discontinuation exceeding 14 consecutive days or 21 days overall

Participants *may* be withdrawn from the *study intervention* for any of the following reasons:

- Repeated incidents of relevant hypotension or tachycardia
- Repeated temporary discontinuation of study intervention
- Vision threatening complication or progression to PDR

Necessity to withdraw the participant from the study will be assessed case by case by the investigator.

09 FEB 2023 Page: 45 of 95

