Repeat or unscheduled samples may be taken for safety reasons or for technical issues with the samples.

After signing an informed consent, participants will be invited to a screening visit, Visit 1, to evaluate their eligibility for this study. Eligible patients with NPDR who meet all of the inclusion criteria and none of the exclusion criteria, will be randomized to treatment with either runcaciguat or placebo. During the treatment period, participants will be monitored for adverse events and concomitant medication, and undergo the assessments outlined in the SoA, Section 1.3.

The treatment period comprises Visits 2 to 15 (Week 1 to Week 49), the End-of-Treatment visit.

An End-of-Study visit, Visit 16, is planned approximately 28 days after last administration of study drug.

- The maximum amount of blood collected from each participant over the duration of the study, including any extra assessments that may be required, will not exceed 300 mL.
- Repeat or unscheduled samples may be taken for safety reasons or for technical issues with the samples.

09 FEB 2023 Page: 48 of 95

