#### 4.1.5 Adverse events

For the purpose of date imputation, the treatment follow-up period date is defined as the last available visit date including unscheduled visits after the EoS visit.

If the start or stop time of the AE is missing completely, the duration of the AE will be calculated based on the start and stop date. If only the start or stop minutes are missing, the duration will be calculated based on the dates and hours. If the start date is partially missing, the first day of that month will be used when only the day is missing. If the stop date is partially missing, the last day of the month will be used when only the day is missing. If both the day and the month are missing, the date will be missing.

Imputed dates will only be used for summary tables. Listings will contain the original entries.

TEAEs are AEs that occurred after first dosing and existing pre-dose AEs that worsened in severity post-dose during the main treatment period until 28 days after the last dose of the study drug.

To determine if an AE is treatment-emergent the following rules will be applied considering a worst-case scenario:

- If the date and time of AE start are completely missing, the AE will be considered as treatment-emergent unless the stop date and time suggest otherwise
- If the time of AE start is missing, but the start date (day, month, and year) of the AE is known, the AE will be considered as treatment-emergent if the AE start date is between the date of treatment start and the date of treatment end plus 28 days (both included), unless the stop date and time of the AE (or other information) suggest otherwise
- If the time and day of AE start are missing, but the month and year is known, the AE will be considered as treatment-emergent if the month of AE start is between the month of treatment start and the month of treatment end date plus 28 days (both included), unless the stop date and time of the AE (or other information) suggest otherwise
- If the time, day, and month of AE start are missing, but the year is known, the AE will be considered as treatment-emergent if the year of AE start is between the year of treatment start and the year of treatment end date plus 28 days (both included), unless the stop date and time (or other information) suggest otherwise.

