#### 4.1.6 Medical history

Completely or partially missing end dates will not be imputed. For imputation of missing diagnosis date, the following rules will be applied:

Page: 17 of 35

MH start date	Imputation rule
Only the day is missing	Impute the date as minimum of first day of the
	month and treatment start date - 1
Month and day are missing	Impute the date as minimum of July 1 st of the
	year and treatment start date - 1
Start date is completely missing but parts of the	Impute the start date as minimum of (July 1st of
stop date are available, or medication is ticked	the year of the initial visit and the treatment start
as ongoing	date - 1)

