#### 6.2 Appendix 2: Baseline characteristics and demographics

Demographic data and baseline characteristics will be presented for total and each treatment group in the FAS, PPS, SAF, and PKS (if different). Summary statistics will be provided for quantitative demographic data and baseline characteristics, including

- Age
- Weight
- Height
- BMI
- HbA1c
- eGFR
- BCVA score
- OCT CRT

Frequency statistics will be provided for qualitative data, including

- DRSS of study eye (stratification criterion)
- Study eye
- Sex
- Race
- Ethnicity
- Smoking status,
- Alcohol consumption
- Caffeine consumption
- Country

Diabetic retinopathy history will be summarized separately:

- Duration of diabetic retinopathy (difference between the reported onset date and the patient's date of randomization).
- N (%) of patients reporting a history of type 1 and type 2 diabetes mellitus.
- Duration of diabetes mellitus type 1 and type 2 (difference between the reported onset date and the patient's date of randomization).
- N (%) of patients reporting a history of arterial hypertension, myocardial infarction, transient ischemic attacks, stroke, and diabetic nephropathy.

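### Two SAP date-imputation rules give wrong or self-contradictory dates: a fully missing last dose can fall on the follow-up visit, and a treatment-emergent adverse event can be dated before first dose

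*SAP*

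**What the plan says.** **Last dose.** SAP 4.1.3 has three rows for a last-dose date that is missing or incomplete. If only the day is missing, the date becomes the last day of the month. If day and month are missing, it becomes the last day of the year. Both are then cut back to the earliest of that date, death and "the last visit date before follow-up". If the date is entirely missing, the rule is "Impute last dose date as minimum of (the date of death, or the last visit date) but no earlier than the date of first dose". This third row does not exclude follow-up.

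On the visits themselves, Protocol Section 8 says: "An End-of-Study visit, Visit 16, is planned approximately 28 days after last administration of study drug". Protocol 6.6 provides no study drug after the planned treatment period or after early withdrawal of treatment. For a participant who stops drug permanently, Protocol 7.1.1 says: "The participant remains in the study for continued assessment of study outcomes following the visit schedule in section 1.3".

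**Adverse-event start.** For a partly missing start date, SAP 4.1.5 says "the first day of that month will be used when only the day is missing". The same section sets the treatment-emergent flag by month when the day is unknown. The month of first dose counts, unless the stop date or other information points the other way. Imputed dates are for summary tables only. SAP 4.5.2 assigns each event to the dose level on which it began and divides by exposure time at that level.

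**The concern.** In the last-dose table, the row with the least information has the loosest limit. A last dose dated to Visit 16 contradicts the schedule, which places that visit about four weeks after dosing has ended. The last-dose date feeds the exposure tables, the denominators of the incidences per 100 participant-years in SAP 4.5.2, the 28-day treatment-emergent window, and the derived end-of-treatment value in SAP 4.1.2. If it also serves as the date of treatment discontinuation, it decides two more things: which values are dropped from summaries under SAP 4.1.4, and whether an end-of-treatment DRSS counts as taken within 4 weeks of discontinuation in the primary analysis (SAP 1.1 and 4.2.2).

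In the adverse-event rules, the date and the flag come from different logic. An event can be declared treatment-emergent and also carry a start date on which the participant had received nothing. The dose-level table then has no cell for it.

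**Working it through.** The plan gives no figure of its own here, so the check applies each rule literally.

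**Inputs.** Protocol Table 1-4: Visit 9 is Day 85, Visit 11 Day 141, Visit 13 Day 225, Visit 15 (end of treatment) Day 337, Visit 16 Day 365. First dose is Day 1. DRSS photography after baseline is scheduled only at Visits 9, 12 and 15. Follow-up is read as Visit 16, as SAP 4.1.4 labels it.

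**1. Completer, last dose entirely missing.**
- Treatment length: 337 − 1 = 336 days = 48 weeks, which matches the plan.
- Rule as written: Day 365. With the limit used in the other two rows: Day 337.
- Excess: 365 − 337 = 28 days; 28/336 = 8.3%.
- Treatment-emergent window: closes on Day 365 + 28 = 393 instead of 337 + 28 = 365. Protocol 8.3.1 collects events only to about that point, so for a completer the main effect is on exposure.

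**2. Participant who stops drug on Day 141 and attends every visit.**
- Entirely missing: 365 − 141 = 224 days too late.
- Day and month missing: at most 337 − 141 = 196 days, when Day 337 falls in the calendar year of the last dose. Otherwise 31 December is the limit. With first dose on 15 March 2022, 31 December is Day 292, so the overrun is 292 − 141 = 151 days.
- Only the day missing: the imputed date stays within the true month, so at most 31 − 1 = 30 days.
- In the entirely missing case the true window closes on Day 141 + 28 = 169, but the imputed one runs to Day 393. Every event reported up to the last visit becomes treatment-emergent.

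**3. The DRSS case.** Suppose drug stops on Day 141, the end-of-treatment visit foreseen at that point is not done, the participant leaves the study at Day 225 with a DRSS at that early-discontinuation visit, and the last-dose date is blank.
- True gap: 225 − 141 = 84 days, more than 4 weeks. SAP 4.2.2 then uses the last grade before discontinuation, here Visit 9 (Day 85).
- Imputed last dose is Day 225 if no later visit takes place. The gap is 0 days, and the off-drug grade is used.

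This assumes that the discontinuation date is taken from the imputed last-dose date, which the SAP does not settle.

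**4. Adverse event, day missing, in the month of first dose.**
- The imputed start is the 1st. It precedes first dose unless first dose was itself on the 1st.
- Over a non-leap year: 365 − 12 = 353 of 365 possible first-dose dates, 96.7%. The gap is 1 to 30 days, mean about 15.
- Example: first dose 15 March 2022, event in March 2022. The imputed start is 1 March, 14 days before first dose. The flag is treatment-emergent. The dose level on 1 March is none. For an event that truly began on treatment, duration is overstated by at least 14 days.

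**The case against.** **The trigger should be rare.** Protocol 6.4 requires intervention start and stop dates, tablet counts and drug accountability, and Protocol 7.1.1 asks for an end-of-treatment visit when drug is stopped. This stands: neither document gives a rate of missing dates, and the trial-level effect cannot be sized.

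**The primary endpoint is largely protected.** A reader might infer that a Visit 16 grade enters the primary analysis. It cannot, because no DRSS is scheduled there. The 4-week test applies to dropouts, whom SAP 4.1.4 describes as leaving the study prematurely, so a participant who stops drug and attends to the end does not meet it on that reading. What remains is the early leaver in step 3.

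**The adverse-event flag is deliberate.** SAP 4.1.5 calls it a worst-case rule and allows it to be overridden, and listings keep original entries. Events are collected from consent, and a pre-dose event that worsens after dosing is treatment-emergent by definition. A reader might therefore call the imputed start impossible, but a pre-dose start is not impossible in itself. The defect is a mismatch between date and flag for new onsets, and the flag needs no change.

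**Diabetes duration.** SAP 4.1.6 places a wholly missing onset of an ongoing condition no later than the day before treatment and no earlier than the enrolment year. A reader might infer that "Duration of diabetes mellitus type 1 and type 2" in SAP 6.2 would then show long-standing disease as new. The documents do not support this: SAP 6.2 computes duration from the reported onset date, and nothing shows that an imputed date enters that table.

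**Conclusion.** The point holds for two rules, as a minor one.

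The entirely-missing row of SAP 4.1.3 is inconsistent with the two rows beside it, and for a completer it adds 28 days (8.3%) of exposure that the schedule rules out. Copying the other rows' limit would not cure it for participants who stop early and stay in the study: the month-missing row can also run months late. It would be wrong to say that all three rows do so, since the day-missing row is bounded at 30 days. The effect on incidence rates has no fixed direction for early stoppers, because a longer exposure and a longer event window act against each other.

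In SAP 4.1.5, nearly every new-onset event with an unknown day in the first-dose month gets a start before first dose while flagged treatment-emergent. The consequence is confined to event durations and the dose-level tables.

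Effects per participant can be large, but the number affected is unknown and probably small. The DRSS consequence further requires an early leaver, a late discontinuation-visit grade, a blank last-dose date and use of that imputed date in the 4-week test.

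**What to change.** 1. SAP 4.1.3, all three last-dose rows: add a cap at the earliest of the recorded date of permanent discontinuation, the end-of-treatment visit and death, and keep the floor at first dose. State that the 4-week DRSS test uses the recorded discontinuation date. If none is recorded, the cap alone does not resolve step 3, so the masked data review should settle the status of that grade.

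2. SAP 4.1.5: for events flagged treatment-emergent as new onsets with only the day missing, set the start to the later of the 1st of the month and the first-dose date, unless the stop date or other information shows a pre-dose onset. Leave the flag rule and the listings unchanged. SAP 4.1.3 already uses the same device for first dose, taking the later of randomization and the 1st of the month.

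The cost is two wording edits and the matching derivation code before unmasking. No new data are needed.
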